## Improving Southeast Florida's Transit Ecosystem for Students

Version 1.3 June 22, 2021

- 1. Project Summary (3 sentences or less): Florida Atlantic University (FAU) will lead a collaboration with two area colleges and three transit agencies to plan, launch, and evaluate transportation solutions for 6,000 students in Fort Lauderdale, Boca Raton, and Davie. Local students who use transit often face lengthy travel and wait times due to inadequate bus and train schedules, while many more students who buy vehicles spend their limited incomes on car payments, gas, insurance and vehicle maintenance in a highly congested region. Of the 140,000 students at the three participating institutions, more than 40% received Pell grants, and more than 50% are students of color.
- 2. Objectives: The overall goal of the project is to evaluate a program to help students from disadvantaged backgrounds achieve success in college. The Kresge Foundation has identified transportation-related issues as one of the barriers facing minority and first-generation students that make it more difficult for students to attain their educational goals. By opening up a broader range of more affordable transportation options to south Florida campuses, this project endeavors to facilitate information on transportation alternatives, thus mobilizing more resources toward attaining academic goals. As a corollary objective, the researchers will conduct research on a recruitment method (see Student Ambassador Sub-Study).

The Cluster Randomized Controlled Trial (cRCT) portion of the study will focus on evaluating the use of information, marketing, and incentives to shape student travel behavior to campus through the three channels identified in Ajzen's (1991) framework (Error: Reference source not found).

We will evaluate whether a package of information, marketing, and incentives shifts student travel behavior to campus over one year, and in turn if these shifts in travel behavior result in improved academic performance.

Specific objectives of the cRCT include evaluating whether the intervention results in relatively:

- 1. Greater utilization of travel modes alternative to single-occupant vehicle travel (transit, biking, walking, bike-sharing, electric scooters, and carpooling)
- Lower rates of car ownership
- 3. Superior college performance (higher GPAs)
- 4. More credit hours completed
- 5. Higher retention rates

PLEASE SEE: RCT Evaluation Protocol for full details.

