# (e) Analysis Plan

From the data collected above in (b) **Research Methods**, we will derive the following major outcome variables, relevant to each of the major research questions:

- 1. Will students in the intervention group, subject to information, marketing incentives as delivered through a MaaS app, be more likely to use alternative modes to reach campus?
  - a. Students who always take alternative modes to campus
  - b. Students who sometimes take alternative modes to campus
  - c. Students who always take an automobile to campus
- 2. Will students in the intervention group, subject to information, marketing incentives as delivered through a MaaS app, reduce their level of car reliance?
  - a. Student car ownership
  - b. Single-occupant vehicle travel
- 3. Will students who make more frequent use of alternative modes to campus and/or reduce car ownership have improved school performance?
  - a. Grade point average
  - b. Credit hours earned
  - c. Retention, degree completion, drop out status, and/or transfer status, as relevant

TATI	1588924-5		
	Approved On	July 22, 2021	
Institutional Review Board	Expires On:	Not Applicable	

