Bivariate analyses will be conducted between each ordinal outcome (i.e. changes in transportation: from less green to green, or green to less green; grades) and demographic and commuting characteristics at baseline using logistic or ordinal logistic regression. Bivariate analyses between longer scale continuous variables (i.e. numeric grade point average) and demographic and commuting characteristics will be determined using linear regression. Associations between continuous outcomes and continuous covariates will be assessed using Pearson or Spearman Rank correlations. Covariates for which bivariate analyses result in p-values less than .20 for baseline and other covariates will be included in an initial mixed-effects (hierarchical) models along with variables and interactions that have been specified by content experts a priori. A monitored step-wise procedure will be used to eliminate covariates from the initial model: that variable with the highest non-significant p-value (p>.05) will be eliminated (provided it is not part of an interaction effect). The final model will include significant variables as well as those determined a priori to control in every model (i.e. distance from residence to public transportation). Models with different covariance structures will be assessed, and that with the lowest Akaike Information Criterion will be chosen. Should these models not converge, generalized estimating equations will be used.

PLEASE SEE: RCT Evaluation Protocol for full details.

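### Three of five objectives promise the intervention's effect on academic outcomes, but the analysis plan asks only a non-randomised travel-to-performance question and does not bar follow-up travel from a GPA model by arm

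*Protocol*

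**What the plan says.** Section 2 (Objectives) introduces its numbered list with "Specific objectives of the cRCT include evaluating whether the intervention results in relatively" and then gives five results. Numbers 3 to 5 are GPA, credit hours and retention. The sentence before the list states a second aim: whether shifts in travel lead in turn to better academic performance. The Dissemination section plans a paper on the academic impact of the app and its accompanying marketing and information.

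Section 4(e) (Analysis Plan) has three research questions. Questions 1 and 2, on mode use and car reliance, are framed by intervention group. Question 3 is the only academic one: "Will students who make more frequent use of alternative modes to campus and/or reduce car ownership have improved school performance".

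The modelling paragraph of section 4(e) gives one rule for building models. Ordinal outcomes are screened against demographic and commuting characteristics measured at baseline. The next sentence carries no such limit: "Bivariate analyses between longer scale continuous variables (i.e. numeric grade point average) and demographic and commuting characteristics will be determined using linear regression". Entry is then defined by "Covariates for which bivariate analyses result in p-values less than .20 for baseline and other covariates will be included", alongside terms that content experts specify in advance. Removal is stepwise: "that variable with the highest non-significant p-value (p>.05) will be eliminated", unless the variable is part of an interaction. Last, "The final model will include significant variables as well as those determined a priori to control in every model", with distance from home to public transport as the only term named. The paragraph refers to the RCT Evaluation Protocol, which is not at hand, for full details.

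**The concern.** An effect of the intervention on GPA is identified by comparing the randomised arms. Question 3 compares students by what they chose to do after randomisation, so its answer mixes any effect of travel with whatever makes some students travel differently. The protocol names two such factors itself: section 4(a) says that campus and full-time or part-time status were chosen as strata because they influence both travel mode and school performance. A team that followed section 4(e) as written would answer three of the five objectives with a confounded comparison, and the planned paper on the app's academic impact would have no matching analysis question.

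If the team does fit GPA by arm, the same covariate rule is the only guide it has here. Because that rule is not limited to baseline variables, follow-up travel could be screened in. Travel is what the intervention is meant to change, so adjusting for it would change the quantity that the arm coefficient estimates.

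**Working it through.** The protocol gives no effect size, standard deviation or intracluster correlation for these outcomes, so there is no stated figure to reproduce. The check is mainly textual.

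**Step 1. Objectives against analysis questions.**

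| Section 2 objective | Question in section 4(e) | Compared by |
|---|---|---|
| 1. Alternative modes | 1 (and 2b) | Arm |
| 2. Car ownership | 2a | Arm |
| 3. GPA | 3a | Travel or car ownership |
| 4. Credit hours | 3b | Travel or car ownership |
| 5. Retention | 3c | Travel or car ownership |

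Three of five objectives have no by-arm question.

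**Step 2. Can follow-up travel reach a GPA model under the rule?** Section 4(b) collects travel at baseline and in each of two semesters, and GPA for each semester, so the variable will exist. The sentence on numeric GPA has no baseline limit, and the entry sentence covers baseline *and other* covariates. Nothing excludes follow-up travel, and nothing says it will be used. If it is a candidate, the .05 rule keeps it when it predicts GPA, which is what question 3 hypothesises.

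**Step 3. What would happen to the arm coefficient.** In linear models, let
- θ = total difference in GPA between arms,
- a = difference in follow-up travel between arms,
- b = slope of GPA on travel given arm.

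The arm coefficient without travel is θ. With travel in the model it is θ − a × b. This holds whether b is causal or only reflects a common cause. It applies to GPA and credit hours. For a binary retention outcome in a logistic model the arithmetic differs, but the adjusted coefficient again has a different meaning.

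**Step 4. Illustration; every input is assumed.** With a = 0.125 to 0.17 SD and b = 0.05 to 0.10 (both in SD units), the shift runs from 0.125 × 0.05 = 0.006 to 0.17 × 0.10 = 0.017 SD of GPA.

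A second set has a = 0.2 SD of travel, a causal slope β in GPA points per SD, residual GPA SD 0.8, and an unmeasured common cause with loading u on both variables. Then b = β + 0.8 × u². A simulation (6,000 independent students, 1:1, 400 replicates) agrees with the formula:

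| θ | β | u | b | a × b | θ − a × b | Simulated |
|---|---|---|---|---|---|---|
| 0.10 | 0.25 | 0 | 0.250 | 0.050 | 0.050 | 0.051 |
| 0.05 | 0.25 | 0 | 0.250 | 0.050 | 0.000 | 0.000 |
| 0.05 | 0.25 | 0.3 | 0.322 | 0.064 | −0.014 | −0.015 |
| 0.05 | 0.25 | 0.5 | 0.450 | 0.090 | −0.040 | −0.041 |
| 0.00 | 0 | 0.3 | 0.072 | 0.014 | −0.014 | −0.015 |

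Travel passed both thresholds in every replicate. The 6,000 is the project's reach in section 1 ("transportation solutions for 6,000 students"), not a derived sample size. Clustering is ignored; it would widen the standard errors but leave the identity unchanged. The table shows that the shift can be small, can remove the whole effect, or can reverse its sign. It does not estimate what this trial would see.

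**The case against.** **Question 3 answers a stated aim.** This is correct. Section 2 asks whether travel shifts improve performance, and question 3 fits that aim. Section 4(e) also introduces its list as outcome variables relevant to the research questions, not as a set of models, and it names GPA, credit hours and retention. A reader who infers that question 3 is misplaced, or that the academic outcomes were forgotten, goes too far. What remains is that no question in section 4(e) compares those outcomes by arm.

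**The missing baseline limit may be an ellipsis.** The same phrase about demographic and commuting characteristics appears in two consecutive sentences, and carrying the limit over from the first is a natural reading. *Other covariates* also has an innocent use, because question 3 needs travel as its exposure. A reader might infer that the plan prescribes adjusting the arm effect for follow-up travel. It does not; it only fails to exclude it.

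**Kept terms may be fixed elsewhere.** Section 4(e) allows for terms chosen in advance and refers to the RCT Evaluation Protocol. A reader might infer that leaving the strata to selection costs power or inflates the type I error. The available figures do not show that: in a simulation with assumed inputs (1,500 independent students), power with selected against fixed strata was 0.786 against 0.788 and 0.771 against 0.772, and rejection under the null was 0.051 to 0.055. Nor does the text show that the arm term could be dropped, since the elimination rule is about covariates.

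**No power loss can be claimed.** Any such figure would rest on invented effect sizes and on a total effect set by the analyst. That stands, and none is claimed here.

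**Conclusion.** The point holds in two parts of unequal strength. The first is firm and rests on the text alone: objectives 3 to 5 and the planned paper promise an intervention effect, while the only academic question in section 4(e) is a non-randomised comparison that cannot deliver it. The second is conditional: the covariate rule leaves follow-up travel open as a candidate in a GPA model by arm, and if it entered, the arm coefficient would move by a × b. The size of that shift is unknown.

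Naming the strata as always kept is a prespecification gain at no real cost, not the correction of a demonstrated error. The point should be fixed. Confidence is moderate, because the RCT Evaluation Protocol may already settle these terms.

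**What to change.** 1. In section 4(e), add a question that compares GPA, credit hours and retention by randomised arm, to match objectives 3 to 5.
2. For arm comparisons, limit covariates to those measured at baseline: add the baseline limit to the sentence on continuous outcomes, and remove the reference to other covariates for these models.
3. State that arm and the randomisation strata (campus, full-time or part-time) stay in every arm model, with the baseline level of the outcome where it is already collected.
4. Report question 3 in a separate model, labelled non-randomised.
5. If the RCT Evaluation Protocol already fixes these terms, align section 4(e) with it.

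The cost is mostly wording. Primary campus and enrolment status are in the Student Performance Data Set, and baseline travel is surveyed. With four campuses and two enrolment statuses, the strata use 3 + 1 = 4 degrees of freedom as main effects, or 4 × 2 − 1 = 7 as full strata. Section 4(b) does not say that semesters before enrolment are retrieved, so prior GPA should be included only if the records already supply it.

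### The step-wise rule in Protocol section 4(e) does not exempt the randomised arm, so as worded it could drop a non-significant arm and lose its estimate and confidence interval

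*Protocol*

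**What the plan says.** The modelling paragraph of section 4(e) works in three steps.

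- **Entry.** Covariates with a bivariate p-value below .20 enter an initial mixed-effects model, "along with variables and interactions that have been specified by content experts a priori". The screening is of "demographic and commuting characteristics at baseline using logistic or ordinal logistic regression" (for continuous outcomes, by linear regression or correlation). The a priori variables and interactions are not listed.
- **Elimination.** "A monitored step-wise procedure will be used to eliminate covariates from the initial model". The rule is that "that variable with the highest non-significant p-value (p>.05) will be eliminated (provided it is not part of an interaction effect").
- **Final model.** "The final model will include significant variables as well as those determined a priori to control in every model". The only one named is given in brackets: "i.e. distance from residence to public transportation".

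The arm appears in none of the three steps. It is, however, the subject of the research questions in the same section. Question 1 begins "Will students in the intervention group, subject to information, marketing incentives as delivered through a MaaS app, be more likely to use alternative modes", and question 2 asks whether the intervention group reduces its car reliance. The objectives in section 2 are all worded as results of the intervention, including those on GPA, credit hours and retention. Section 4(a) stratifies the randomisation by campus and by full-time or part-time status. The modelling paragraph does not name these factors as retained either.

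**The concern.** A rule that keeps a term only if it is significant is a debatable way to choose adjustment variables. It is unsuitable for the treatment term, because whether the main result appears would then depend on its own p-value. An outcome with a non-significant arm would have no estimate and no interval in the final model, so a reader could not tell an effect near zero from one measured imprecisely. Arm effects that did appear would have passed a significance filter and would be too large on average.

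The interaction exception does not solve this. An arm kept only because it is part of an interaction would, under reference coding, carry the effect at the reference level of the other variable. That is not the overall effect that questions 1 and 2 ask about.

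**Working it through.** The Protocol gives no power, effect size, SD or ICC for this point, so there is no figure of its own to reproduce. The check has two parts.

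**1. Following the rule for the arm**

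- *Can the arm enter the model?* The bivariate screen covers baseline demographic and commuting characteristics, and the arm is neither. Its only evident route in is the unlisted set of a priori variables.
- *Is it exempt from elimination?* Being specified a priori gives entry. The elimination step exempts only a variable that is part of an interaction, and no arm interaction is named.
- *Is it kept at the end?* The final model admits significant variables and a priori controls. A non-significant arm is not in the first group. It is in the second only if someone has put it there, and the one control named is an adjustment variable.

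So if the arm is treated as one of the model's variables, it can be removed. If it is not, the paragraph never places it in a model at all. The text needs the same addition on either reading.

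**2. Size of the effect, if the rule is applied to the arm**

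Inputs: the p>.05 threshold from section 4(e). Assumptions: a two-sided test (the Protocol does not say), the arm's Wald statistic Z ~ Normal(θ, 1), and true power of 50%, 80% or 90%. The critical value is c = 1.96.

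- P(kept) = Φ(θ − c) + Φ(−θ − c), and P(deleted) = 1 − P(kept).
- Average surviving estimate relative to the truth = [θ + φ(c − θ)/Φ(θ − c)] / θ. The wrong-direction tail is negligible at these powers.

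| Case | θ | P(deleted) | Mean surviving Z | Ratio to truth |
|---|---|---|---|---|
| No effect | 0 | 0.95 | – | – |
| 50% power | 1.960 | 0.50 | 1.960 + 0.3989/0.50 = 2.758 | 2.758/1.960 = 1.41 |
| 80% power | 2.802 | 0.20 | 2.802 + 0.2800/0.80 = 3.152 | 3.152/2.802 = 1.12 |
| 90% power | 3.242 | 0.10 | 3.242 + 0.1755/0.90 = 3.437 | 3.437/3.242 = 1.06 |

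A simulation of 2,000,000 draws per case gave ratios of 1.407, 1.125 and 1.060. It also showed that, under no effect, none of the surviving 95% intervals contains the true value of zero.

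With the arm forced into the model, P(deleted) is 0 at every θ and the filter disappears.

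**The case against.** The strongest objection is that this paragraph selects adjustment variables around a fixed treatment comparison. The procedure is said to eliminate covariates, the screened candidates are baseline characteristics, and silence about the arm is not a rule to delete it. This is a fair reading. A reader might infer that the Protocol deletes the arm whenever p>.05, but the documents do not support that. The text never says so, it exempts variables in interactions, and it calls the procedure monitored. What remains is that the elimination and final-model sentences speak of variables without limit, and no sentence sets the treatment term apart.

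A reader might also infer that distance to public transportation is the only variable kept regardless of significance. That goes too far as well. The a priori set is described in the plural, and the Protocol uses i.e. loosely elsewhere: the list of travel modes under Application Data opens with it and closes with etc. The arm could therefore belong to the set. Still, the example given is an adjustment variable, and the set is described as variables to control for, which does not naturally describe the exposure.

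Third, section 4(e) refers to an RCT Evaluation Protocol that is not at hand, and the handling of the treatment term is often left to a SAP. Silence alone would not be a finding. Here, though, the Protocol states a retention rule, and that rule as worded conflicts with the questions it serves. There is also no rule that only final-model terms are reported, so the loss of null estimates is a likely consequence and not a stated one.

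Finally, the figures are general properties of a significance filter. Apart from the 5% threshold they use nothing from this trial. That is correct, and they are given here only as conditional values.

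**Conclusion.** The concern holds in a limited form. Section 4(e) fixes a p-value rule for what stays in the final model and does not exempt the randomised arm, although the arm is the effect asked for in section 2 and in questions 1 and 2. The rule as worded could therefore remove a non-significant arm, together with its estimate and interval.

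The size is conditional on the rule being applied to the arm, which the text neither states nor rules out. In that case, deletion would occur in about 95% of models under no effect and 20% at 80% power, with average inflation of the surviving estimates of about 1.12 at 80% power and 1.41 at 50% power. These values assume a two-sided 5% test and a normally distributed statistic. The wording should be settled before the outcome data are analysed, because afterwards the choice between readings could follow the results.

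**What to change.** Add the following to the modelling paragraph of section 4(e):

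- For every analysis of the intervention's effect (the section 2 objectives and questions 1 and 2 of section 4(e)), the randomised arm and the stratification factors, campus and full-time or part-time status, are in every model and are exempt from screening and elimination.
- The arm effect is taken from the model without arm interactions and is reported with its 95% confidence interval whatever its p-value. Arm interactions are reported separately.
- Question 3, whose exposure is travel behaviour or car ownership, remains a separate analysis in which that exposure is likewise kept in the model.

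The third item matters because a blanket instruction to report the arm effect as the answer for each outcome would replace question 3 with a different question. The RCT Evaluation Protocol should be checked for agreement. The cost is a few sentences, with no extra data and no change to the sample size.

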#### 4. Research Plan

# (a) Research Design

This study is designed as an unblinded cluster randomized controlled trial (cRCT) in which a cluster of students who live in a particular residence off-campus will be randomly assigned to either the MaaS app or no app; students in a cluster assigned to the MaaS group will also receive information concerning housing options. Cluster randomization will be stratified by campus and whether the student is full or part-time; these stratification factors were chosen because of their influence on student travel modes and school performance. Cluster randomization will use a 1:1 ratio.

The trial will be conducted over one year. A pilot study of 200 students will test the randomization process on the responses from the Informed Consent survey. The pilot will be used to determine a likely response rate to the survey and to identify issues with the survey rollout. PLEASE SEE: RCT Evaluation Protocol for full details.

I	1588924-5		
	Approved On	July 22, 2021	
ĺ	Expires On:	Not Applicable	

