# (b) Research Methods

The Mobility-as-a-Service (MaaS) App will be provided to students in the Intervention Group and is intended to facilitate their use of alternative transportation modes such as public transit, ride-hailing, walking, biking, bike share, and e-scooter share to get to campus. The MaaS App will be downloaded to students' smartphones and will provide real-time, multimodal trip planning to students on demand when they open the app. This means, for instance, that a student can plan a trip that includes driving to a train station, taking the train, and then walking from the alighting train station to their final destination. The app will be white label, i.e. it will have a customized look and feel specific to the participating south Florida colleges, and it will have personalization features so that students can tailor the app to their travel patterns.

PLEASE SEE: RCT Evaluation Protocol for full details.

The Cluster Randomized Controlled Trial (cRCT) portion of the study will focus on evaluating the use of information, marketing, and incentives to shape student travel behavior to campus through the three channels identified in Ajzen's framework (Error: Reference source not found).

There will be three sources of quantitative data: 1) student surveys will provide information on student travel behavior; 2) official academic records will provide data on student academic performance; and 3) student app usage will be derived directly from the app.

Student travel behavior for both intervention and control populations will be collected through regular surveys conducted at baseline and each of the two semesters (See Appendix 4 – Student Travel Behavior Survey for the full survey text). We will issue a baseline travel behavior survey at the beginning of the project and then issue regular surveys during fall and spring semesters for the one-year observation period.

We will also ask questions regarding the students' demographics, a few questions about attitudes towards alternative modes and self-reported BMI and health related quality of life, and a few questions concerning their suggestions for potential improvements for travel to campus.

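### Lowest AIC chooses the covariance structure without fixing residence, the unit of randomisation, as a retained level, so the standard error of the arm effect may be understated

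*Protocol*

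**What the plan says.** Protocol section 4(a) makes the residence the unit of allocation: "a cluster of students who live in a particular residence off-campus will be randomly assigned to either the MaaS app or no app". It adds that "Cluster randomization will use a 1:1 ratio".

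Section 4(b) makes the travel data longitudinal, with "regular surveys conducted at baseline and each of the two semesters". Responses can therefore be correlated in two ways: between students at the same address, and within a student over time.

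Section 4(e) puts the covariates that pass screening into hierarchical models: they "will be included in an initial mixed-effects (hierarchical) models along with variables and interactions that have been specified by content experts a priori". It does not say what the levels are. The covariance rule follows: "Models with different covariance structures will be assessed, and that with the lowest Akaike Information Criterion will be chosen". The candidate structures are not listed. The terms protected from elimination are covariates fixed in advance, and the one example is distance from home to public transport. The fallback is stated in one sentence: "Should these models not converge, generalized estimating equations will be used". The section then refers to a separate RCT Evaluation Protocol, which is not at hand.

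**The concern.** When residences are randomised, the precision of the arm comparison depends on variation between residences. The design settles that; model fit does not. AIC asks a different question, namely whether a variance component improves the likelihood enough to pay for its parameter. With one extra parameter it keeps the component only if twice the log-likelihood gain exceeds 2. A real but modest residence component, estimated from small residences, can fail that test.

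There is a second route. Responses from one student in two semesters are usually far more alike than responses from two housemates. If a student-level structure and a residence-level structure compete as alternatives, AIC will prefer the student-level one even when residence matters. The word hierarchical does not rule this out, because a student random effect alone makes a repeated-measures model hierarchical.

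In either case, students who share an address and an allocation would count as independent evidence on the arm effect. Travel mode and car ownership are plausibly similar within a household, so the correlation need not be small.

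**Working it through.** The protocol gives no power calculation, ICC or residence size, so there is no figure of its own to reproduce. Everything below rests on assumed values: m is participants per residence, ICC is the residence correlation, and the test is two-sided at nominal 5%.

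**1. Residence omitted, one outcome per student.** Design effect DE = 1 + (m − 1) × ICC. Actual type I error = 2 × (1 − Φ(1.96/√DE)).

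| m | ICC | DE | 1.96/√DE | Type I error |
|---|---|---|---|---|
| 1.1 | 0.05 | 1.005 | 1.955 | 5.1% |
| 2 | 0.10 | 1.10 | 1.869 | 6.2% |
| 5 | 0.05 | 1.20 | 1.789 | 7.4% |
| 3 | 0.20 | 1.40 | 1.656 | 9.8% |
| 10 | 0.05 | 1.45 | 1.628 | 10.4% |
| 20 | 0.05 | 1.95 | 1.404 | 16.0% |

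**2. Student-only and residence-only structures compete on AIC.** Two semesters per student, total variance 1, within-student correlation r = 0.5 (which includes the residence ICC), no true arm effect, equal numbers of parameters, 3,000 simulated trials per row. As a check, the variance of a student's two-semester mean is (1 + r)/2 = 0.75. Under the student-only structure the neglected design effect is therefore 1 + (m − 1) × ICC/0.75, which goes into the formula of step 1.

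| Residences × m | ICC | Student structure chosen | Simulated type I error | DE | Formula |
|---|---|---|---|---|---|
| 1,000 × 2 | 0.10 | 100% | 6.2% | 1.133 | 6.6% |
| 500 × 5 | 0.05 | 100% | 8.1% | 1.267 | 8.2% |
| 1,000 × 3 | 0.20 | over 99.9% | 12.4% | 1.533 | 11.4% |
| 600 × 10 | 0.05 | 100% | 12.2% | 1.60 | 12.1% |

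Simulation and formula agree within simulation error. The last row has 6,000 students, so a large trial gives no protection on this route. The residence-level model, if always used, gave 4.4-5.8% in these simulations.

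**3. AIC decides only between with and without a residence random intercept.** Single continuous outcome, balanced residences, no arm effect, 20,000 simulated trials per setting, m = 2, 5 or 10, ICC 0.01-0.30. The setting with the highest overall type I error at each trial size was:

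| Students | Setting | Residence dropped | Overall type I error |
|---|---|---|---|
| 6,000 | 600 × 10, ICC 0.01 | 45% | 5.4% |
| 1,000 | 100 × 10, ICC 0.01 | 82% | 5.7% |
| 200 | 20 × 10, ICC 0.05 | 68% | 7.3% |

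At 6,000 students the mean standard error was at least 0.991 of the true one in every setting, and residence was never dropped at an ICC of 0.10 or more. With residence always kept, type I error was 4.7-5.2% across all settings.

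**The case against.** The strongest reply concerns the reading. The models are called hierarchical, the trial is described as cluster randomised by residence, and surveys repeat over semesters. A natural reading is that residence stays and AIC picks only the structure over time, which is a proper use of AIC. Naming random effects and clustering units is also commonly left to an analysis plan, and the unseen RCT Evaluation Protocol may do so. This stands as far as it goes: a reader might infer that the plan discards residence, and the document does not say that. But the protocol is not merely silent. It commits to a selection rule, exempts nothing from it, and so allows an invalid analysis as readily as a valid one.

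On size, a reader might take the frequent dropping of residence as proof that intervals will be too narrow. Step 3 does not support that: AIC drops the term mostly when it matters little, and visible inflation needed few residences. Nor is the 6-16% range the error rate of the AIC rule as such; it applies only if the chosen structure has no residence term. If a model with both levels is among the candidates, inflation is small.

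Cluster sizes may also be small. The 6,000 students in the project summary (a programme figure, not a derived trial size) are 6,000/50,912 = 11.8% of the off-campus population in section 4(c). If students enrolled independently, four co-enrolled neighbours (m = 5) would need about 4/0.118 = 34 other eligible students at the address, and m = 20 about 19/0.118 = 161. Housemates may enrol together, so this is not a bound, but the largest sizes would need something like an apartment complex treated as one residence.

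Finally, the simulations use continuous, balanced data, whereas travel mode is categorical and car ownership is a status. The direction carries over; the exact percentages may not.

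**Conclusion.** The point holds in conditional form. Section 4(e) does not protect the level at which section 4(a) randomises, in either the mixed model or the GEE fallback, and so the standard error of the arm effect may be understated. It does not follow that it will be.

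Which of the two ranges in the working applies depends on the candidate set: about 5-7% when AIC judges only whether to add residence, and about 6-16% when the selected structure has no residence term. Both rest on assumed residence sizes and ICCs. With about one participant per residence, neither route matters. The change is worth making because the design already answers the question that AIC is being allowed to decide, and because settling it costs little under every assumption.

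**What to change.** Amend the covariance sentence in section 4(e) to say three things:

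- A random effect for the residence as randomised is kept in every model that estimates the arm effect, whatever its AIC or estimated size.
- AIC is used only to choose the within-student structure across semesters.
- Any GEE fit clusters on residence and uses robust standard errors.

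If the RCT Evaluation Protocol already says this, align the wording of section 4(e) with it. The cost is a short text change, and slightly wider intervals where residences hold several participants. Where residences are nearly all single participants, the results will hardly change.
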